10.1.2 Tumor Specimen Evaluation

MSKCC Homologous Recombination Repair (HRR) Assay

At MSKCC we have been very interested in measuring the proficiency of homologous repair in cancer cells as a correlate of subsequent treatment sensitivity. Although this current study is clearly a phase I study to understand the tolerability of rucaparib, we will collect correlative data with the intention of establishing the feasibility of our research methods and identifying testable hypotheses for larger subsequent patient cohorts. One of our primary research hypotheses, which we are evaluating across multiple studies, is that pre-existing homologous recombination deficiency (HRD) predict for better clinical outcomes (local control, disease-free survival), while HR proficiency results in treatment resistance. We have recently described our methods for evaluating HR patency in paraffin-embedded archived patient specimens as an alternate to our earlier assay based on the quantification of RAD51 foci in cancer cells subjected to ex-vivo ionizing radiation. In our original assay²³, we used fresh tumor specimens from which a single cell suspension was created, half of which was irradiated, and the other half mock-treated. Cell nuclei were then analyzed for the formation of γH2AX, BRCA1, and RAD51 in both irradiated and un-irradiated cells using confocal microscopy. In our alternate method, we have shown that exome sequencing to evaluate the status of a panel of candidate HR genes as well as evaluation for previously described structural signatures associated with HRD [(large-scale state transitions (LST), telomeric regions with allelic imbalance (htAI), large segments with loss-of-heterozygosity (LOH)], can accurately predict for HRD²⁴. In particular bi-allelic inactivation in one or more HR DNA repair genes was found to be significantly associated with functional HRD and with higher LST scores. Our treatment cohort will be unique in that we will have access to 1) original pre-treatment diagnostic cores 2) post-chemotherapy residual disease cores 3) germline DNA.

Formalin-fixed, paraffin-embedded (FFPE) core needle specimens will be retrieved and transported to the MSKCC Integrated Genomics Operations (IGO) core ([name], Core Facility Head). Using standard molecular biology techniques, DNA will be extracted using the DNeasy kit (Qiagen, Valencia, CA) to isolate genomic DNA and whole exome sequencing will be performed. This will allow us to look at LST (large-scale state

transitions), ntAI, LOH as well as our previously defined list of 95 HR effectors or regulators. To assign tumors to the HR proficient vs deficient categories, we will begin by screening for high LST scores. Patients with high LST scores will then be evaluated for bi-allelic inactivation in one or more HR related genes. Patients with evidence of both suggestive structural alterations AND bi-allelic loss in a candidate HR gene on their diagnostic core specimens will be scored as HRD. All other patients will be scored as HR proficient. We will also perform sequencing on the post-therapy residual, and stratify patients by receipt of platinum agents. We will compare the mentioned parameters of HRD in pre and post-therapy specimens. Our provisional hypothesis is that our cohort of non-responders will be enriched for HR proficiency compared to unselected TNBC tumors or HR+ tumors.

Immune Correlates

A large body of research using experimental animal models indicates that the immune system controls the development of cancer through immune surveillance mechanisms²⁵. Histologic analyses of solid malignancies reveal that they are infiltrated by various cells of the innate and adaptive immune system²⁶. Therapeutic modulation of the immune system for clinical benefit in cancer patients has been demonstrated by numerous modalities, including antibody blockade of inhibitory molecules, adoptive T cell transfer, and autologous cell-based vaccines²⁷⁻²⁹. A recent large-scale meta-analysis of the correlation of tumor infiltrating T cells with survival clearly establishes that a relative high density of TH1 and cytotoxic memory T cells correlated with a favorable prognosis in the majority of cancers³⁰.

Tumor infiltrating lymphocytes (TILs) may be a useful histological predictor of benefit from chemotherapy in breast cancer patients, although it has not been established whether or not response to chemotherapy would be specific to a class of chemotherapy. Specific to breast cancer, the evaluation of TILs has been shown in the GeparSixto (GBG 66) trial to be relevant for response to chemotherapy in triple negative and Her2-positive early breast cancers^{31,32}. In this analysis, a lymphocyte predominant pattern of infiltrate was predictive of a complete pathologic response to neoadjuvant chemotherapy. Similarly, the association of TILs and response to trastuzumab and chemotherapy (epirubicin/cyclophosphamide with docetaxel +/- capecitabine) was evaluated in 156 HER2+ patients from the neoadjuvant GeparQuattro trial³³. TILs were associated with higher responses to the trastuzumab and chemotherapy combination, and tumor-mediated immunosuppression was evident in the lymphocytic infiltrate, with PD-1 and IDO1 significantly predictive of trastuzumab benefit.

The prognostic value of TILs has also been validated in a combined analysis of two Phase III randomized adjuvant breast cancer clinical trials^{32,34-37}. In these studies, the percentage of intratumoral and stromal lymphocytes in pre-treatment tumor biopsies was found to be an independent predictor of pCR in both the training and validation cohorts. Higher TIL pathologic scores were associated with a better prognosis: for every 10% increment in stromal TIL, a 14% reduction of risk for recurrence or death was observed (p=0.02), and for every 10% increment in intratumoral TIL, a 28% risk reduction was seen (p=0.06). Multivariate analysis confirmed stromal TIL to be an independent prognostic marker of disease-free survival.

Collectively, these data suggest that the natural course of breast cancer as well as the response to therapy is linked to the degree by which the tumor is recognized by the immune system. Response to radiotherapy may be also be predicted by the level of TIL, however data supporting this in breast cancer is scant. In squamous cell carcinoma of the head and neck as well as rectal cancer however, TILs can predict response to combination chemoradiotherapy^{38,39}. The induction of an immune response by radiotherapy may also have important consequences. Several studies have shown the various mechanisms by which RT stimulates the immune system. One effect of localized tumor irradiation is the exposure of a large amount of tumor antigens in the form of necrotic and apoptotic tumor cells⁴⁰. The contexts in which these antigens are presented to the immune system are also impacted by tumor irradiation. Tumor radiotherapy leads to an inflammatory tumor microenvironment by inducing the expression of several proinflammatory cytokines⁴¹. In addition, upregulation of major histocompatibility molecules and costimulatory molecules can potentiate effector cytolytic T cell responses⁴².

The pretreatment core specimens from this study will allow for the comprehensive assessment of TILs which will be correlated to response. Participants in this study are by definition incomplete responders to cytotoxic chemotherapy, and we would anticipate proportionally lower TILs compared to unselected or responding patients. Data from patients on our other trials or projects will serve as controls and will allow us to compare TIL profiles. We will perform RNA sequencing of these specimens for the TIL expression signature as another assessment of pre-existing TILs. This will provide important insight into the role of the tumor immunity in the response to chemoradiotherapy. In addition the assessment of homologous recombination can also factor into the endogenous response of the immune system to the tumor as well as response to therapy. The effect of homologous recombination on tumor immunity is not well characterized, however the induction of microsatellite instability as a pathway of carcinogenesis has clearly been linked to tumor immune response⁴³. Tumor cells with deficient DNA mismatch repair develop microsatellite instability and the resulting tumors are densely infiltrated by TILs⁴⁴. It is suggested that mismatch repair deficiency leads to numerous insertion/deletions that ultimately translate to the generation of tumor-specific neopeptides that can then be recognized by the immune system⁴⁵. Radiation administered to a tumor with an underlying homologous recombination defect may lead to significant “epitope spreading” resulting in the induction of an immune response against newly recognized tumor associated antigens. This study will begin to address the immune consequences of tumor genomic instability. There is currently no accepted methodology for quantitatively scoring TILs in core biopsies before neoadjuvant chemotherapy. We will arbitrarily define tumors with stromal TILs greater than 20% as being positive for TILs.

Cell-free DNA Collection for circulating tumor DNA

For patients consenting to 12-245, we will collect ctDNA at 3 time points: baseline (within 30 days of starting treatment), week 3 of RT+rucaparib, and then at week 10. ctDNA has been shown to correlate with treatment response in several tumor types including in breast cancer⁴⁶.

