2.0 OBJECTIVES AND SCIENTIFIC AIMS

- The primary objective is to determine the maximum tolerated dose of rucaparib that can be administered concurrently with standard doses of radiotherapy to the breast/chest wall +/- regional nodes.
- Secondary objectives are:
 - To describe the nature of toxicity that develops when rucaparib is administered concurrently with RT.
 - To assess locoregional relapse and distant relapse.
 - To evaluate biomarkers (HRD status) correlated with locoregional relapse following rucaparib administered concurrently with RT.
 - To evaluate the presence of tumor infiltrating lymphocytes (TILs) and correlate this with locoregional relapse.
 - To assess patient reported satisfaction and quality of life with treatment using the Breast Cancer Treatment Outcomes Scale (BCTOS)
 - To determine the rate of poor cosmetic outcomes from both provider and patient perspectives up to 2 years after rucaparib + RT using the RTOG (Radiation Therapy Oncology Group) cosmesis scale² and digital images.

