Under the CRM paradigm, the relationship between dose and toxicity is summarized by a single-parameter (α) logistic model that represents the assumed relationship prior to the collection of any patient data. Information about the relationship between dose and toxicity can be summarized using the distribution of the parameter, updated according to the current data. For instance, we can estimate the probability of toxicity at assigned doses and the subsequent target dose as a function of α based on the current data. The toxicity results will be summarized as follows.

The distribution of α updated according to the current data and the corresponding dose-toxicity model will be calculated. Predictive intervals concerning the toxicity parameter will be provided using this updated distribution of α .

The posterior distribution of toxicity, which display the probability a future patient will experience toxicity at a given dose based on the current data, will be calculated for each tested level. The dose level of rucaparib that produces the target rate of toxicity will be determined from this.

The proportion of subjects encountering toxicity at each dose level will be reported.

Analysis of Secondary Endpoints

Toxicity profiles will be tabulated and summarized. Locoregional relapse and distant relapse will be estimated using Kaplan-Meier methods.

Correlations between locoregional and distant relapse with HRD status (deficient vs proficient) and stromal TILs (present vs absent) will be evaluated using Kaplan-Meier estimates and a log-rank test. Patient satisfaction, quality of life, and cosmetic outcomes will be summarized descriptively and graphically. Note, for the cosmesis outcome based on the RTOG scale as provided in the appendix, excellent and good cosmesis will be grouped together, and fair and poor will be grouped together. The rate of fair/poor cosmesis will be calculated and described. All statistical analyses of secondary endpoints are considered to be exploratory in nature as the sample size is expected to be small in this phase I study. Analyses will be done over all 30 patients accrued to the study and by dose cohort.

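### Stromal TILs are analysed only as above or below an arbitrary 20% cut, with no effect size; a hazard ratio per 10% with its interval should be added

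*Combined protocol and SAP*

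**What the plan says.** Section 2.0 lists the TIL analysis among the secondary objectives: "To evaluate the presence of tumor infiltrating lymphocytes (TILs) and correlate this with locoregional relapse". Section 10.1.2 (Immune Correlates) fixes the cut: "We will arbitrarily define tumors with stromal TILs greater than 20% as being positive for TILs". The reason given is that no quantitative scoring method is accepted for core biopsies taken before neoadjuvant chemotherapy. Section 14.0 (Analysis of Secondary Endpoints) relates locoregional and distant relapse to HRD status and to TILs, and for the latter says: "stromal TILs (present vs absent) will be evaluated using Kaplan-Meier estimates and a log-rank test". It names no hazard ratio, interval, trend test or continuous analysis.

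The background in section 10.1.2 gives a prognostic effect on a graded scale: "for every 10% increment in stromal TIL, a 14% reduction of risk for recurrence or death was observed". The same section says of this cohort that "we would anticipate proportionally lower TILs compared to unselected or responding patients". It gives no mean, spread or expected share above 20%.

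Section 14.0 also qualifies the analysis: "All statistical analyses of secondary endpoints are considered to be exploratory in nature as the sample size is expected to be small". On the analysis set it says: "Analyses will be done over all 30 patients accrued to the study and by dose cohort". No event target, power or significance level is set for TILs.

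**The concern.** A percentage that must be judged in order to apply the rule is reduced to yes or no at a value chosen without data. Only a test and two curves are planned. A log-rank test gives a p-value but no effect size, and in a trial this small the p-value alone says little.

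Section 10.1.2 says the correlative data are meant to show feasibility and to suggest hypotheses for larger cohorts. An estimate with an interval on a recognisable scale serves that purpose better than a p-value from an arbitrary split. If few patients lie above 20%, the split may also leave a group with no relapses, from which no finite hazard ratio can be estimated. What is at stake is the usefulness of one secondary objective. The MTD is unaffected.

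**Working it through.** The plan states no power, event count or TIL distribution for this analysis, so it has no figure to reproduce. Four checks follow, with assumptions marked.

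**1. Information kept by the split.** For a small log-linear effect, the information kept relative to a linear analysis is the squared correlation between TIL and the indicator of TIL > 20%. For normal TILs with share q positive this is φ(z)²/[q(1−q)], where z is the upper-q normal quantile.
- q = 0.5: 0.3989²/0.25 = 0.637, so 36% is lost.
- q = 0.2: 0.2800²/0.16 = 0.490, so 51% is lost.
- q = 0.1: 0.1755²/0.09 = 0.342, so 66% is lost.

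TIL percentages are bounded and probably right-skewed (assumption). Over the same range of q, the loss is 35%–52% for exponential, 38%–52% for lognormal and 24%–37% for beta distributions. Over all these cases it is about 24% to 66%. The upper end needs near-normal TILs and only about 10% positive.

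**2. Expected locoregional events.** Section 3.1 gives 26% at five years for triple-negative patients without a complete response. Assume this applies to all 30 patients at a constant hazard.
- Yearly hazard: −ln(0.74)/5 = 0.0602.
- By two years, the planned follow-up: 30 × (1 − e^(−0.1204)) = 3.4 events.
- By five years: 30 × 0.26 = 7.8 events.

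The working range is therefore about 3 to 8, and the upper end needs follow-up beyond the planned two years. Patients without usable tissue would reduce it.

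**3. Power at the background effect.** Take a hazard ratio of 0.86 per 10%, a TIL SD of 10 to 25 points (assumed) and a two-sided 5% level (assumed). With D events and b = |ln 0.86| × SD/10, power = Φ(b√D − 1.96) + Φ(−b√D − 1.96). For the split, b is multiplied by the square root of the information kept (normal TILs, 10%–50% positive).

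| Events | Continuous | Split |
|---|---|---|
| 3 | 5.8%–10.0% | 5.3%–8.2% |
| 8 | 7.1%–18.7% | 5.7%–13.6% |

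Events needed for 80% power with the continuous covariate are (1.96 + 0.84)²/b²: 346 at SD 10 and 56 at SD 25. Simulated trials of 30 patients with exponential TILs and about 4 to 8 events gave 2%–8% for continuous and 2%–10% for the split, with no consistent advantage. A gain appeared only under a much stronger assumed effect. At a hazard ratio of 0.60 per 10% and about 9 events, power was 13% against 6% with 20% positive.

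**4. Chance of no relapse in the TIL-positive group.** With exponential TILs and a hazard ratio of 0.86 per 10%, that group carries a share q × 0.86² of the total hazard. At q = 0.2 this is 0.2 × 0.7396 = 0.148. Treating the event count as Poisson, the chance of no event in the group is e^(−D × share).

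| Share positive | 3.4 events | 7.8 events |
|---|---|---|
| 10% | 78% | 56% |
| 20% | 60% | 32% |
| 30% | 47% | 18% |
| 50% | 28% | 6% |

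Simulation agrees: with 20% positive, 58% of trials had an empty group at about 4 events and 30% at about 8.

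**The case against.** The other side has a good deal. Section 14.0 already labels the secondary analyses exploratory because the sample is small. The cut is openly called arbitrary and is fixed in advance, so it is not data-driven. The objective is worded as the presence of TILs. The background is mixed: section 10.1.2 also cites a categorical, lymphocyte-predominant pattern as predictive of complete response. The cited 14% reduction concerns recurrence or death in adjuvant trials, so a per-10% hazard ratio here would match its covariate scale but not its endpoint or population. A percentage score without an accepted method is also a weak basis for a linear model. If the true effect were a threshold near 20%, the split would lose little. A penalised model could give a finite estimate for the binary variable too, although with an empty group the penalty would largely determine it.

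These points limit the severity. They also rule out some stronger readings. A reader might infer that the split is known to discard a third to two thirds of the information. That needs normal TILs, 10%–50% positive and a log-linear effect, none of which the documents give. A reader might infer that the cut will leave few positive patients. The protocol expects lower TILs than in unselected or responding patients but states no level, so this is only possible. A reader might also take the continuous analysis to be free. It needs no new tissue, but the plan does not say that the percentage is recorded, and the model adds assumptions.

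What the objections do not justify is planning no effect estimate at all for a named objective. The lack of an accepted scoring method weakens the 20% rule as well.

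**Conclusion.** The concern holds as a minor improvement to an exploratory analysis. The plan tests TILs only at a self-declared arbitrary cut and reports no effect size, while its background effect is graded. The loss of information is about a quarter to two thirds if the effect is roughly log-linear, under TIL distributions that are assumed.

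It would be wrong to conclude that a continuous analysis would make the TIL question answerable. With about 3 to 8 locoregional events, neither approach is informative at a hazard ratio of 0.86 per 10%, and no power gain is shown. The case rests on estimability and interpretation. If about 20% of patients are positive, the binary contrast has roughly a 30% to 60% chance of an empty group. A penalised continuous model still yields a finite estimate and an interval, provided at least one relapse occurs. The event count rests on applying 26% at five years to everyone at a constant hazard. No rate is given from which to repeat the check for distant relapse in this population.

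**What to change.** In section 14.0, state that the stromal TIL percentage is recorded for each evaluable core. Add a Firth-penalised Cox model with stromal TIL per 10% as a continuous covariate, and report the hazard ratio and confidence interval as the main exploratory TIL estimate. Keep the 20% split for the Kaplan-Meier display and the log-rank test.

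State the limits alongside: an assumed linear effect on the log hazard, sensitivity to a few high values, reliance on a percentage score with no accepted method, and few expected events. Report the number of patients and relapses on each side of the cut, so that an empty group is visible.

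The cost is a few sentences and, if the percentage is not already captured, one data field. No extra tissue, visits or patients are needed.

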11.0 TOXICITIES/SIDE EFFECTS

11.1 Toxicities of Study Intervention

Toxicities of Radiation Therapy

Anticipated toxicities include radiation skin reaction, as well as possible radiation pneumonitis or pericarditis (which may also occur in the absence of a radiosensitizing agent when breast/chest wall and nodal radiotherapy is administered). Treating investigators should manage any toxicities that develop using standard medications, such as topical agents for skin reaction and steroids for pneumonitis.

Toxicities of Rucaparib

Rucaparib is an FDA-approved agent for treatment of patients with deleterious BRCA mutation (germline and/or somatic) associated advanced ovarian cancer who have been treated with two or more chemotherapies. It is investigational for use in TNBC and HR+ breast cancer. A comprehensive list of toxicities may be found in the investigator's brochure. Principal side effects of rucaparib are listed in Table 11A.

Table 11A Principal side effects of Rucaparib

Central Nervous System	Fatigue, dizziness
GI	Nausea, decreased appetite, diarrhea, vomiting, elevated ALT/AST, dyspepsia, elevated blood cholesterol
Heme	Anemia, febrile neutropenia; decreased WBC, , neutropenia; thrombocytopenia elevated creatinine
Miscellaneous	Fever, lymphopenia

11.2 Dose Modifications

Radiation therapy may be withheld due to acute toxicity at the discretion of the treating investigator without being considered a dose-limiting toxicity if the treatment break is no greater than 5 days. All radiation treatment breaks should be recorded, including details regarding duration of break and reason.

Rucaparib dose will not be modified on this study. Treatment with rucaparib should be held if any of the following are observed:

Table 11B

Toxicity	Rucaparib Treatment Action	Timing for Restarting Rucaparib Treatment
----------	----------------------------	-------------------------------------------

Confluent moist desquamation (single, contiguous region of moist desquamation that exceeds 25cm ² in area)	Record DLT	Discontinue rucaparib
Any toxicity requiring a radiotherapy dose delay exceeding 5 business days	Record DLT	Discontinue rucaparib
Grade 3 or 4 hematologic toxicity Includes defined DLTs: Absolute Neutrophil count <1,000/mm ³ (with or without fever) Platelet count <50,000/mm ³ Hemoglobin <8.0 g/dl	Record DLT	Discontinue rucaparib
Grade 3 or 4 non-hematologic toxicity Except for: 
• alopecia, nausea, vomiting, or diarrhea adequately controlled with systemic antiemetic/antidiarrheal medication administered in standard doses according to the study center routines• Grade 3 ALT/AST elevation (see below)	Record DLT	Discontinue rucaparib
Grade 4 ALT/AST elevations	Hold rucaparib	Restart treatment when values have returned to ≤ Grade 2. Monitor liver function tests weekly for 3 weeks after reintroduction of rucaparib. Any toxicity requiring a radiotherapy dose delay exceeding 5 business days should be recorded as a DLT and rucaparib discontinued.

Grade 3 ALT/AST elevations	Continuation of rucaparib with elevation of ALT/AST up to Grade 3 is permitted provided: 
• bilirubin is < ULN• alkaline phosphatase is < 3x ULNand• there are no other signs of liver dysfunction	Monitor liver function tests weekly until resolution to ≤ Grade 2. If patient has Grade 3 ALT/AST and continues on rucaparib, and levels do not decline within 2 weeks or they continue to rise, treatment interruption and resolution to ≤ Grade 2 will be required before rucaparib can be resumed at current dose.
Grade 2 toxicity not adequately controlled by concomitant medications and/or supportive care.	Hold rucaparib upon investigator discretion	Restart drug, per investigator discretion, at assigned study dose level (no dose reduction). Note: any toxicity requiring a radiotherapy dose delay exceeding 5 business days should be recorded as a DLT and rucaparib discontinued. Drug holds exceeding 5 business days will be reviewed by the PI and discussed by the study team and the treating physicians. If the patient restarts Rucaparib after a break, missed doses will not be made up. The patient will take Rucaparib until the conclusion of the initially scheduled 10 weeks.

